5. CRITERIA FOR EVALUATION

5.1 Primary Endpoints

1. Absolute change in FEV₁ % predicted with standard colistin TID dosing versus PK-adjusted colistin BID dosing, with APE treatment.
2. Absolute change in FEV₁% predicted with standard tobramycin daily dosing versus PK-adjusted colistin BID dosing, with APE treatment.

3. Absolute change in FEV1% predicted with standard tobramycin daily dosing versus standard colistin TID dosing, with APE treatment.
4. Safety of standard colistin TID dosing versus PK-adjusted colistin BID dosing in APE treatment, based on assessments of clinical symptoms, AKI occurrences during treatment (based on KDIGO criteria), change in urine protein:creatinine ratios, and an FDA approved renal injury biomarker test, Nephrocheck®, which measures: TIMP2 and IGFBP-7 (Astute Medical).
5. Safety of standard tobramycin daily dosing versus PK-adjusted colistin BID dosing or standard colistin TID dosing in APE treatment, based on assessments described in #4.

5.2 Secondary Endpoints

1. Time to therapeutic colistin dosing and number of therapy interruptions due to changes in creatinine with standard colistin, modified colistin, and standard tobramycin dosing.
2. Total number of IV doses delivered over the course of APE treatment.
3. Change in sputum microbiology profile following treatment with colistin versus tobramycin.
4. Number of exacerbations in the ensuing year and time to first pulmonary exacerbation following APE treatment.
5. Absolute change in Cystic Fibrosis Questionnaire-Revised (CFQ-R) respiratory domain score before and after APE treatment.
6. Number of episodes of neurotoxicity and ototoxicity in study arms, based on case-report form.
7. Colistin peak, mid-point, and trough during APE, for calculations of area under the curve (AUC).

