Pilot study of PK parameters in an adult CF cohort with APE: We assayed steady-state pharmacokinetic and pharmacodynamic properties of intravenous colistin in CF subjects >18 years old admitted for APE treatment, during the first week of admission. The primary objective of the study was to determine PK parameters, specifically clearance (CL), volume of distribution (VD), area under the curve (AUC), and maximal concentrations (Cmax). A total of 16 CF subjects were evaluated. All subjects received IV colistin on a standard dosing schedule, in conjunction with other anti-Pseudomonal antibiotic agents, dosed three times daily. Patient characteristics are depicted in Table 1. Steady state plasma concentrations were obtained after \geq 2 days of therapy during week 1 of admission, and subjects underwent phlebotomy at 0, 0.5, 1, 2, 4, and 6 hours after administration. Peak, midpoint, and trough colistin A and B concentrations (active drug) were measured utilizing liquid chromatography-mass spectrometry (LC-MS) technology^{21,22}. As seen in Table 1, the mean study age of 32 is older than mean ages in prior studies of IV colistin in CF subjects^{19,20}. Mean FEV₁ % predicted was 40% predicted at onset of exacerbation, demonstrating that the drug can be given safely with severe airflow limitation. There were no reported side effects of chest tightness that would limit its use. Two subjects experienced SCr rises of \geq 0.3 mg/dL, necessitating discontinuation of drug. Mean colistin dosing was 3.42 mg/kg/d over 15 days. A PK analysis of

Table 1: Characteristics of colistin PK pilot study subjects

No. of subjects	16
Gender- no. (% female)	8 (50)
Age (mean \pm SD years)	32 \pm 13
Sputum culture	
Pseudomonas aeruginosa only	8 (50)
Pseudomonas aeruginosa, Staphylococcus aureus, and/or other GNR	8 (50)
Concomitant systemic antibiotic therapy- no. (%)	
β -lactam, carbapenem, monobactam, or quinolone	16 (100)
vancomycin or linezolid	5 (31)
FEV ₁ (mean \pm SD % predicted)	40 \pm 15
Mean dose colistin- mg/kg/d (mean \pm SD)	3.42 \pm 0.6
Mean duration of therapy-days (mean \pm SD)	15 \pm 9
Baseline SCr- mg/dL (mean \pm SD)	.77 \pm .27
Number with AKI (% with $>$ 0.3 mg/dL increase in SCr)	2 (13)
SCr- serum creatinine	
AKI- acute kidney injury	

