Standard tobramycin arm: Subjects receive IV tobramycin 8-10 mg/kg/day (X-gen Pharmaceuticals) with once daily dosing for 14 days. Peaks and troughs are drawn with the second dose of tobramycin, and the drug is infused over 30 minutes. Dose adjustment will occur to achieve non-detectable troughs and peaks 20-30 mg/dL². Tobramycin concentrations are assessed once weekly during each week of APE treatment.

8.4.3 Dose modification: Subjects active in the study who experience moderate to severe toxicity will undergo dose adjustments as follows. If clinical providers and site investigators believe that it is appropriate to have the subject continue in the study, this will be allowed. If study drug is discontinued, the data acquired prior to its discontinuation will be utilized in the analysis.

1. Tobramycin will be discontinued if ototoxicity occurs (patient complains of ringing in ears and/or hearing loss).
2. Tobramycin will be held with increases of creatinine >0.3 mg/dL. If creatinine increases are not reversible, the drug is discontinued. If they are reversible, the drug may be resumed at lower dosing or longer intervals, at the discretion of the physician and the clinical pharmacist in joint consultation.
3. Colistin will be discontinued for serious episodes of neurotoxicity, such as debilitating headache, seizure, and neuromuscular weakness.
4. Colistin will be held for one dose and then resumed at a lower dose if creatinine rises \geq 0.3 mg/dL from baseline. If creatinine fails to recover or continues to rise, the drug will be discontinued. Patients who do not undergo PK measurements are maintained at the highest dose achievable (between 3-5 mg/kg/day) without renal insufficiency (< 0.3 mg/dL increase in serum creatinine).

8.4.4 Study drug preparation, handling and dispensing: Appropriately trained pharmacy personnel and nursing staff are responsible for the administration of medications. Medications are dispensed and labeled in accordance with federal and local state Board of Pharmacy regulations.

8.4.5 Administration instructions: Instruction of hours of administration, dose, and duration of administration will be transmitted from the National Jewish Health | Saint Joseph Hospital inpatient pharmacists to CF pulmonary floor nursing staff. Drugs will be administered through indwelling peripherally inserted central catheters (PICC) or indwelling ports.

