[name] will monitor the data collection for accuracy and quality for the study. Data will be collected from subject medical and research records and maintained in electronic Case Report Forms (eCRFs) using REDCap (Research Electronic Data Capture), a secure web-based application that supports data capture for research studies.

15. Statistical Methods and Considerations

15.1 General: Summary statistics will be calculated for demographic and baseline characteristics (age, sex, genotype, diabetic status, FEV₁ % predicted) time to therapeutic dosing for PK-adjusted colistin versus tobramycin, number of therapy interruptions between study arms, and total number of IV antibiotic doses. Study medications and exposure to study drug data will be summarized in contingency tables. Summary statistics and changes from admission visit to end of treatment will be presented for FEV₁ % predicted and questionnaire results, on an intent-to-treat basis, including all subjects receiving at least three days of colistin or tobramycin, and at least one efficacy assessment. Subjects will be enrolled once.

15.2 Efficacy analysis: We will perform equivalence testing to show similarity of colistin treatments, as well as for colistin vs tobramycin treatments. For both comparisons, confidence intervals for difference in FEV₁ changes from pre to post treatment time points will be constructed, and equivalence tests to within 5% will be performed. These will be derived from linear mixed models fitted for FEV₁ that include a random intercept for subjects to account for repeated measures, and the following covariates: age, other medication, admits in the previous year, and diabetes. Nested random terms will be included in the model to account for repeated measures – one for subject and one for visit within subject. CFQ-R domain scores will be analyzed in a similar fashion. Times to next pulmonary exacerbation and occurrence of neurotoxicity between standard colistin and PK-adjusted colistin will be analyzed using the Kaplan-Meier method. Subsequent pulmonary exacerbations in the ensuing year for all enrolled subjects, as well as antimicrobial resistance to tobramycin and colistin before and after treatment, will be summarized. Unless otherwise noted, 2-sided tests will be used with $\alpha = 0.05$.

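### The count of creatinine-driven therapy interruptions does not separate a temporary hold from a permanent stop, so it can understate treatment lost to kidney toxicity

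*Combined protocol and SAP*

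**What the plan says.** Section 5.2, endpoint 1, includes the "number of therapy interruptions due to changes in creatinine with standard colistin, modified colistin, and standard tobramycin dosing". The synopsis carries the same item. Section 15.1 (and the matching synopsis text) lists the "number of therapy interruptions between study arms" among quantities to receive summary statistics, with no model and no adjustment for time on drug.

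Section 8.4.3 gives a creatinine rise two possible outcomes.

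- Tobramycin: "Tobramycin will be held with increases of creatinine >0.3 mg/dL. If creatinine increases are not reversible, the drug is discontinued". Otherwise, "If they are reversible, the drug may be resumed at lower dosing or longer intervals".
- Colistin: "Colistin will be held for one dose and then resumed at a lower dose if creatinine rises" by at least 0.3 mg/dL. Then: "If creatinine fails to recover or continues to rise, the drug will be discontinued".

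The same section adds: "If study drug is discontinued, the data acquired prior to its discontinuation will be utilized in the analysis".

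The documents do not define an interruption, do not say whether a permanent stop is one, and do not rank a stop against a hold. Creatinine-driven discontinuation is not a listed endpoint in section 5.1 or 5.2.

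**The concern.** The endpoint appears intended to show how far kidney toxicity disrupts treatment, which bears directly on the trial's safety question. A count of events does this only if each event costs about the same amount of treatment. Here a one-dose hold and the loss of the rest of the course can carry the same score. The more serious outcome also removes the subject from any further counting. An arm with more permanent stops can then look no worse than an arm with brief, recovering rises, or even better.

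**Working it through.** The plan gives no expected value or power for this endpoint, so there is no figure of its own to reproduce. As a side check on the rates used below, 0.19/0.12 = 1.58, which agrees with the roughly 60% excess stated in section 15.4.

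**Two subjects in the BID colistin arm, 14-day course, 28 planned doses (hypothetical).**

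- Subject A has two recovered one-dose holds. Count 2; doses missed 2/28 = 7.1%.
- Subject B has an unrecovered rise on day 5, and the drug is stopped for the remaining 9 days. Count 1 (0 if neither the hold nor the stop is scored); doses missed 18/28 = 64.3%.

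**Arm level, formula.** Expected count = n × p × [u·c + (1 − u)(1 + m)].

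- From the documents: n = 30 per arm (section 15.4); AKI rate p = 0.19 for tobramycin and 0.12 for colistin (retrospective cohort, section 1.1).
- Assumed, because the documents do not give them: u, the share of AKI subjects permanently stopped; m, the mean number of further holds per resumed subject; c, the score for a stop (0 or 1).
- The formula places the stop at the first AKI episode.

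**Same AKI rate (12%), stop scored 1, no repeat holds.** The count is 30 × 0.12 = 3.6 in both arms, whatever the stop shares. Assume onset is uniform over days 2–14 (mean day 8, so 6 days lost per stop) and each BID hold costs 0.5 day.

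- Stop share 50%: 1.8 × 6 + 1.8 × 0.5 = 11.7 days lost.
- Stop share 10%: 0.36 × 6 + 3.24 × 0.5 = 3.8 days lost.

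The counts are identical and the treatment lost differs about threefold. With m = 0.5 the counts become 3.6 × 1.25 = 4.5 and 3.6 × 1.45 = 5.2, so the arm with more stops scores lower.

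**Different AKI rates (19% versus 12%).**

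| c | m | u at 19% | u at 12% | Count, 19% arm | Count, 12% arm |
|---|---|---|---|---|---|
| 0 | 0 | 0.1 | 0.1 | 5.1 | 3.2 |
| 0 | 0 | 0.5 | 0.1 | 2.9 | 3.2 (reversed) |
| 0 | 0 | 0.7 | 0.1 | 1.7 | 3.2 (reversed) |
| 1 | 0 | any | any | 5.7 | 3.6 |
| 1 | 1 | 0.1 | 0.1 | 10.8 | 6.8 |
| 1 | 1 | 0.5 | 0.1 | 8.6 | 6.8 |
| 1 | 1 | 1 | 0 | 5.7 | 7.2 (reversed) |

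Conditions for reversal:

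- c = 0: (1 − u_high)/(1 − u_low) < 0.12/0.19 = 0.63.
- c = 1, u = 1 versus 0: m > 0.19/0.12 − 1 = 0.58.
- c = 1, u_low = 0.1: u_high > 0.80 at m = 1, and u_high > 0.62 at m = 2.
- Equal stop shares: no reversal under either scoring.

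Short of reversal, the contrast can still shrink. In the c = 1, m = 1, 50% versus 10% row the ratio of counts is 8.55/6.84 = 1.25, against an AKI ratio of 1.58, while permanent stops are 0.19 × 0.5 = 9.5% versus 0.12 × 0.1 = 1.2% of subjects.

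**Do the other measures repair it?**

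- AKI occurrence (section 5.1) does not show whether treatment was briefly held or ended.
- Total IV doses (section 5.2, endpoint 2) depends on schedule. A full 14 days is 42 doses TID, 28 BID and 14 once daily. A TID subject stopped after day 9 has had 27 doses, almost a full BID course.
- Section 15.1 also tabulates drug exposure, but does not tie it to creatinine.

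The hold triggers are also worded differently by drug (above 0.3 mg/dL for tobramycin, at least 0.3 mg/dL for colistin). That wording should be reconciled, but this point does not depend on it.

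**The case against.** The strongest reply is that the count usually ranks the arms correctly and is never read alone. Much of that stands.

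- A reader might infer that a stopped subject scores at most one. The text does not support this. Both rules hold the drug before stopping it, so a subject held, resumed, held again and then stopped can score two or more. For the same reason a score of zero is the least natural reading, and the reversals in the c = 0 rows rest on it.
- A reader might infer that the count must fall as toxicity worsens. It need not. With a stop scored 1 and AKI at 19% versus 12%, even a 100% versus 0% split in stop shares needs more than 0.58 further holds per resumed subject. Resumption of colistin is at a lower dose, which could make repeat holds uncommon.
- A reader might take the pilot in section 1.1, where two of 16 subjects had creatinine rises "necessitating discontinuation of drug", as showing that stopping is the usual outcome. Two subjects cannot show that, and the pilot is not said to have used the trial's hold-and-resume rule. If stopping were usual, repeat holds would be rare and the count would roughly equal the number of AKI cases.
- AKI is a primary safety component with an adjusted comparison in section 15.3. The interruption count is one half of one descriptive secondary endpoint.

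What the reply does not answer is that none of these measures reports how much treatment was lost because of creatinine, or how many subjects were permanently stopped for it.

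**Conclusion.** The concern holds as a measurement defect. The count treats a hold and a permanent stop alike, does not measure treatment lost to kidney toxicity, and can understate disruption in an arm with more permanent stops. In the equal-AKI illustration (stop shares 50% versus 10%, uniform onset, half a day per hold) identical counts conceal about a threefold difference in days lost. Reversal of the arm ranking is possible but conditional: it needs a higher stop share in the more toxic arm and, if a stop scores 1, repeat holds as well. The documents do not support saying that reversal is expected.

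The stop shares, repeat-hold rates and onset distribution are assumptions. At 3.6 to 5.7 expected AKI cases per arm, any summary will be imprecise. The endpoint is secondary and descriptive, so this should be corrected but does not threaten the primary comparisons.

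**What to change.** In section 5.2 endpoint 1, the synopsis and section 15.1, report by arm:

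- (a) the number and percentage of subjects permanently discontinued because of a creatinine change; and
- (b) the percentage of each subject's planned study-drug doses not given because of a creatinine change, counting every planned dose after a creatinine-driven stop as not given.

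Planned doses should follow the assigned schedule and that subject's planned course length. A fixed 14-day denominator would not fit, because the synopsis allows participation of up to 14 days. Where tobramycin resumes at a longer interval because of creatinine, the omitted doses count against the assigned schedule. Define an interruption, and keep the raw count of holds as descriptive.

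Measure (b) counts doses rather than milligrams, so it will not show a dose reduction after a hold.

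Infusions, dose and duration of dosing, and missed doses are already recorded (sections 8.5 and 8.6). The cost is a wording change and slightly more analysis work. No dosing, holding or stopping rule changes.

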6. SUBJECT SELECTION

6.1 Study population

Subjects with a diagnosis of CF who meet all the inclusion and none of the exclusion criteria will be eligible for participation in this study.

6.2 Inclusion criteria:

1. Male or female \geq 18 years of age at Visit 1.
2. Documentation of CF diagnosis as evidenced by one or more clinical features consistent with the CF phenotype and one or more of the following criteria:
 - Sweat chloride equal or greater than 60 mEq/L by quantitative pilocarpine iontophoresis test.
 - Two well-characterized mutations in the CFTR gene
 - Abnormal nasal potential difference (change in NPD in response to a low chloride solution and isoproterenol of less than -5 mV).
3. Documentation of the presence of an acute pulmonary exacerbation, based on CF Foundation guidelines, as diagnosed by a faculty member of the Denver Adult CF Program.
4. Respiratory culture(s) demonstrating evidence of *Pseudomonas aeruginosa* or *Achromobacter species* airway infection.
5. Subject is able to produce sputum, undergo phlebotomy, and provide written consent.
6. The subject's treating physician has determined that they should receive either tobramycin or colistin intravenously as one of the designated agents for their APE

treatment. Subjects who are able to receive either tobramycin or colistin as part of their antibiotic regimen will be randomized into one of three arms. If a treating physician deems that a subject cannot receive tobramycin due to vestibular toxicity, ototoxicity or bacterial resistance, the subject will be randomized to either standard or PK-adjusted colistin.

6.3 Exclusion criteria:

1. Presence of chronic renal insufficiency, with abnormal baseline creatinine >1.2mg/dL.
2. Presence of a condition or abnormality that in the opinion of the investigator would compromise the safety of the patient or the quality of the data.
3. Inability to perform reproducible spirometry.
4. Inability to expectorate sputum.

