SUBJECT SELECTION CRITERIA: INCLUSION CRITERIA	CF patients 18 years or over who are diagnosed with APE based on CFF guidelines, and are chronically infected with P. aeruginosa , or other gram-negative bacteria, can produce sputum, undergo phlebotomy and provide written consent, will be eligible for participation, once their treating physician has determined that they should receive one of the two agents for APE treatment while hospitalized. Subjects able to receive either tobramycin or colistin as part of their IV antibiotic regimen will be randomized to one of three arms. If a treating physician deems that a subject cannot receive tobramycin due to vestibular or ototoxicity or bacterial resistance, the subject will be randomized to either standard or PK-adjusted colistin.

SUBJECT SELECTION CRITERIA: EXCLUSION CRITERIA	Presence of chronic renal insufficiency, with abnormal baseline creatinine >1.2.
TEST PRODUCT, DOSE, AND ROUTE OF ADMINISTRATION	Dosing of IV colistin will be determined based on serum concentrations of the drug on a BID dosing schedule.
CONTROL PRODUCT, DOSE AND ROUTE OF ADMINISTRATION	Dosing of IV tobramycin once daily will occur based on consensus guidelines and will be adjusted based on serum levels. Dosing of IV colistin TID will occur based on product insert (Perrigo Company).
STANDARD OF CARE TREATMENT	All study arms will be receiving APE treatment as a multi-drug therapeutic regimen, based upon CFF guidelines.
DURATION OF SUBJECT PARTICIPATION AND DURATION OF STUDY	Subjects will be on study for up to 14 days, or for the duration of their IV antibiotic treatment for APE while hospitalized. The study will enroll for 36 months.
CONCOMITANT MEDICATIONS	Allowed: Standard therapy for CF pulmonary exacerbations. Prohibited: none

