STATISTICS Primary analysis plan	
Statistical Methods: A detailed statistical analysis report will be written that will describe all analyses, tables, figures, and data listings generated for this study. All analyses will be performed using SAS ® (SAS Institute, Cary, NC, USA).
 
Analysis Populations: All analyses will be performed using an intent-to-treat (ITT) population, which is defined as all randomized subjects. Subjects who are discontinued from the study temporarily or permanently will remain in the analyses population according to ITT.
 
Demographic and Baseline Characteristics: Summary statistics will be calculated for demographic and baseline characteristics (age, sex, genotype, diabetic status, FEV₁ % predicted) time to therapeutic dosing for colistin versus tobramycin, number of therapy interruptions between study arms, and total number of IV antibiotic doses. Study medications and exposure to study drug data will be summarized in contingency tables.
 
Summary statistics and changes from

admission visit to end of treatment will be presented for FEV₁ % predicted and questionnaires, on an intent-to-treat basis, including all subjects receiving at least three days of colistin or tobramycin, and at least one efficacy assessment.

Analysis of Primary Endpoints:

Efficacy analysis: We will perform equivalence testing to show similarity of colistin treatments, as well as for colistin vs tobramycin treatments. For both comparisons, confidence intervals for difference in FEV₁ changes from pre to post treatment time points will be constructed, and equivalence tests to within 5% will be performed. Times to next pulmonary exacerbation and occurrence of neurotoxicity between standard colistin and PK-adjusted colistin will be analyzed using the Kaplan-Meier method. Subsequent pulmonary exacerbations in the ensuing year for all enrolled subjects, as well as antimicrobial resistance to tobramycin and colistin before and after treatment, will be summarized. Unless otherwise noted, 2-sided tests will be used with $\alpha = 0.05$.

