4. STUDY DESIGN

4.1 Study Overview

This is a prospective randomized single center interventional trial enrolling adult CF subjects who are diagnosed with acute pulmonary exacerbations (APE) by their treating

physician and who, according to their treating physician, will receive either tobramycin or colistin for the treatment of *Pseudomonas aeruginosa* or other appropriate gram-negative rods, such as *Achromobacter xylosoxidans*. The study is designed to evaluate a) whether pharmacokinetically adjusted colistin dosing, given on a twice daily schedule, provides a more favorable efficacy and safety profile versus standard colistin three times daily dosing, with no serum levels analyzed, b) whether pharmacokinetic-adjusted twice daily colistin dosing compares favorably to standard once daily tobramycin dosing, based on efficacy and safety, and c) how standard colistin dosing compares to standard once daily tobramycin dosing, based on efficacy and safety, during treatment of APE. The three treatment arms are as follows: 1) standard colistin TID dosing (based on product insert and evidence based recommendations for CF⁵), 2) pharmacokinetic-adjusted twice daily colistin dosing, or 3) standard tobramycin dosing once daily. The premise of the study is that newer, highly accurate analytical techniques, available through the University of Colorado School of Pharmacy have allowed pharmacokinetic (PK) and pharmacodynamic (PD) studies of colistin, in a cohort of adult CF subjects receiving the agent during APE. This has allowed us a new understanding of how the drug is metabolized in CF and how we can optimize its administration.

1. Adult patients will be enrolled at the time therapy is initiated for the treatment of a pulmonary exacerbation of CF.
2. Subjects will be block randomized based on gender, FEV₁%, and time of enrollment, into one of three treatment arms.
3. Patients receiving standard colistin dosing will be treated according to product insert and evidence based recommendations for CF². Patient demographics, medications, and results of standard laboratory tests will be recorded.

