8. STUDY TREATMENTS

8.1 Method of assigning subjects to treatment groups

All subjects will enter the study at the time they are diagnosed with an APE and designated for hospital admission to treat with a drug regimen which includes either intravenous tobramycin or colistin. Block randomization will be utilized based on gender, FEV₁% predicted, and time of enrollment to ensure relatively equal treatment allocation based on these variables.

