15.3 Safety analysis: The safety profile of each colistin arm and the tobramycin arm will be assessed in terms of the following: incidence of acute kidney injury (AKI), incidence of treatment related clinical events (ototoxicity, vestibular toxicity, and neurotoxicity). Adverse event rates will be compared between treatment groups using logistic regression, adjusting for age, medications such as vancomycin, baseline FEV₁, admits in the previous year, exposure to nephrotoxic antibiotics in the previous 5 years, and diagnosis of CF related diabetes (CFRD) as covariates. Repeated measures within subjects will be accounted for by including a random intercept for subjects. Summary statistics and changes from admission will be presented for serum creatinine and urine:protein ratios. The urine protein:creatinine ratio will be assessed as a

biomarker of drug toxicity. There are no published criteria for cessation of therapy or accurate prediction of AKI as a result of the urine protein values. Thus, this data will be analyzed as a predictor for AKI. We will analyze Nephrocheck® assay results in a case control design. Subjects who develop AKI within each of the study arms will have urine thawed and analyzed by Nephrocheck® and those results will be compared to age, gender, and FEV₁ matched control urines obtained from subjects within the study who did not develop AKI. An adjusted odds ratio will be derived from a model fitted with unconditional logistic regression and adjusted for confounding variables. Estimates of odds ratios and 99% confidence intervals will be presented.

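### Subjects who cannot receive tobramycin enter only the colistin arms, yet the plan neither stratifies, adjusts nor restricts for this, so the tobramycin-versus-colistin comparisons are only partly randomised

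*Combined protocol and SAP*

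**What the plan says.** There are two routes into the trial. Under section 6.2, item 6, subjects who can receive either drug are randomised among three arms. If the treating physician judges that a subject "cannot receive tobramycin due to vestibular toxicity, ototoxicity or bacterial resistance, the subject will be randomized to either standard or PK-adjusted colistin". The synopsis has the same rule ("If a treating physician deems that a subject cannot receive tobramycin due to vestibular or ototoxicity or bacterial resistance").

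The sections on allocation and analysis do not carry the second route:

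- Section 4.1, item 2: "Subjects will be block randomized based on gender, FEV₁%, and time of enrollment, into one of three treatment arms".
- Section 8.1: "Block randomization will be utilized based on gender, FEV₁% predicted, and time of enrollment". Tobramycin eligibility is not named.
- Synopsis, Analysis Populations: "All analyses will be performed using an intent-to-treat (ITT) population, which is defined as all randomized subjects".
- Section 15.2, FEV₁ model: a random intercept "and the following covariates: age, other medication, admits in the previous year, and diabetes".
- Section 15.3, safety model: age, concomitant drugs, baseline FEV₁, prior-year admissions, "exposure to nephrotoxic antibiotics in the previous 5 years, and diagnosis of CF related diabetes (CFRD) as covariates".

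Section 5.1 makes tobramycin versus each colistin arm a primary comparison for FEV₁ (endpoints 2 and 3) and for safety (endpoint 5).

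**The concern.** A subject deemed unable to take tobramycin has no chance of allocation to the tobramycin arm. Such subjects can only accumulate in the colistin arms, so the imbalance is built into the design and does not shrink as the sample grows. Blocking on sex, FEV₁ and time cannot remove it.

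The reasons for ineligibility are not neutral. Resistance and earlier ototoxicity plausibly reflect longer antibiotic exposure. Ototoxicity is also an outcome compared between arms (3.2, objective 3; 5.2, item 6). In the retrospective data of section 1.1, colistin recipients had lower FEV₁ (40% versus 50% predicted), more CF-related diabetes (66% versus 38%) and more admissions per year (2.3 versus 1.8). Those figures describe all colistin recipients, not ineligible subjects, but they show that choice of drug followed prognosis at this centre.

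Three of the five primary endpoints would then be reported as randomised comparisons when they are only partly so. The plan provides no analysis that would show how far they are off.

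**Working it through.** The documents give no ineligible share, no outcome difference for ineligible subjects and no FEV₁ SD. There is therefore no stated figure to reproduce on this point, and the scenarios below are assumptions.

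**Inputs from the documents.** Total 90 subjects, 30 per group (15.4); equivalence margin 5 (15.2); retrospective FEV₁ gain 12 versus 9 points and AKI 19% versus 12% (1.1).

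**Assumptions.** k = 10, 20 or 30 of 90 ineligible, split 1:1 between the colistin arms; the rest allocated 1:1:1; SD of FEV₁ change 6, 8 or 10; a difference between ineligible and eligible subjects that remains after covariate adjustment.

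**Make-up of the arms.** Tobramycin n1 = (90 − k)/3. Each colistin arm n2 = n1 + k/2. Ineligible share = (k/2)/n2. Bias = share × residual difference.

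| k | n1 | n2 | Share of each colistin arm | Bias, residual 3 points | Bias, residual 1 to 5 points |
|---|---|---|---|---|---|
| 10 | 26.7 | 31.7 | 5/31.7 = 15.8% | 0.5 | 0.2 to 0.8 |
| 20 | 23.3 | 33.3 | 10/33.3 = 30.0% | 0.9 | 0.3 to 1.5 |
| 30 | 20.0 | 35.0 | 15/35 = 42.9% | 1.3 | 0.4 to 2.1 |

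The share in the tobramycin arm is 0% throughout. The 3-point residual borrows the size of the 12 − 9 gap between drugs; it is not an estimate for ineligible subjects.

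**Effect on the equivalence test.** Equivalence is declared if |d| + t × s × √(1/n1 + 1/n2) < 5. Section 15.2 says "Unless otherwise noted, 2-sided tests will be used" at 0.05 but does not say whether equivalence uses two one-sided 5% tests or a 95% interval, so both are shown. Take k = 20, a true difference of 5 (the margin) and a bias of 0.9. The expected contrast is then 4.1 if the bias masks the difference and 5.9 if it adds to it. Probability of wrongly declaring equivalence, SD 6 / 8 / 10:

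| | No bias | Masking | Adding |
|---|---|---|---|
| One-sided 5% | 5.0 / 4.8 / 2.9% | 13.6 / 10.3 / 5.1% | 1.4 / 1.9 / 1.5% |
| 95% interval | 2.5 / 2.0 / 0.4% | 7.9 / 4.6 / 0.6% | 0.6 / 0.8 / 0.2% |

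At SD 10 even the masking case stays at about the nominal level or below it.

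**AKI.** The retrospective gap is 19 − 12 = 7 points. With k = 20 and an assumed residual of +5 or −5 points in ineligible subjects, it would read 7 − 0.30 × 5 = 5.5 or 7 + 0.30 × 5 = 8.5.

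**The case against.** There are three fair counter-arguments.

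First, each prognostic difference that section 1.1 documents is already handled in part. Diabetes and prior-year admissions are covariates in both models. Baseline FEV₁ is a blocking factor and a safety covariate, and the FEV₁ endpoint is itself a change. Bias needs a further residual effect, and the documents give no evidence of one. This stands as a limit on size. It does not restore randomisation, because none of these variables encodes eligibility.

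Second, the information may be recoverable. Table 3 has an eligibility review at Visit 1, and medical history and the previous 12 months of cultures are also reviewed. Separate two-arm and three-arm schedules may exist in practice. That is plausible, but section 10.1 does not list the determination among the Visit 1 records and no analysis uses it.

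Third, restriction costs precision. At k = 20 and SD 8 the restricted standard error is 8 × √(2/23.3) = 2.34. The pooled analysis has standard error 2.16, and with the 0.9-point bias a root mean square error of √(2.16² + 0.90²) = 2.34, so accuracy is equal. At SD 10 pooling does slightly better (2.85 against 2.93); at SD 6 restriction does (1.76 against 1.85). This is correct, but root mean square error does not protect an equivalence claim. Restriction removes the bias and keeps the error rate at its nominal limit. A milder alternative also stands: keep all subjects and add an eligibility term. Its standard error is 2.25 in the same case, and it requires arm effects to be the same in both groups.

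**Conclusion.** The concern holds. The two routes are explicit, and eligibility appears in none of the blocking factors, covariates or analysis restrictions. Primary endpoints 2, 3 and 5 and the ototoxicity comparison are therefore only partly protected by randomisation. Standard versus PK-adjusted colistin remains fully randomised.

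That defect follows from the text alone. Its size does not. Under the assumed scenarios the FEV₁ contrast shifts by 0.2 to 2.1 points against a margin of 5, in either direction. With 20 ineligible subjects and a 0.9-point masking bias, false equivalence at one-sided 5% rises to about 14% at SD 6 and 10% at SD 8, and stays near nominal at SD 10. It should be fixed, because the correction is cheap and the determination is known before allocation.

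A lesser drafting point: section 2.1 lets subjects who cannot receive colistin be enrolled only to tobramycin, and it omits bacterial resistance as a reason for colistin only. Neither matches the synopsis or section 6.2.

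**What to change.** 1. Record the physician's determination (three arms or colistin only) on the randomisation form before allocation, and name it as a stratum in 4.1 and 8.1.
2. State in 15.2 and 15.3 that tobramycin-versus-colistin comparisons use only subjects randomised among all three arms, and that standard versus PK-adjusted colistin uses both strata, adjusted for stratum. An all-subjects model with an eligibility term could serve as a sensitivity analysis, with its common-effect assumption stated.
3. Restate in 15.4 the expected number per arm for the tobramycin contrasts, and give in 15.2 the confidence level of the equivalence test.
4. Reconcile section 2.1 with the synopsis and 6.2, and say that anyone enrolled to tobramycin without randomisation is outside the intention-to-treat population.

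**Cost.** Some protocol and SAP wording and one form field. The tobramycin contrasts would apply only to subjects eligible for both drugs and rest on about 27 / 23 / 20 per arm for k = 10 / 20 / 30. The standard error rises by 4 / 8 / 13% relative to pooling, from √(2/n1) ÷ √(1/n1 + 1/n2).

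Equivalence power at SD 8 and true difference 0:

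| | 30 per arm | Pooled, if unbiased (k = 10 / 20 / 30) | Restricted (k = 10 / 20 / 30) |
|---|---|---|---|
| One-sided 5% | 55% | 52 / 48 / 42% | 46 / 35 / 24% |
| 95% interval | 33% | 30 / 25 / 19% | 23 / 13 / 6% |

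Keeping 30 three-way-randomised subjects per arm at the same ineligible shares (k/90) would need 90/(1 − k/90), which is about 102 / 116 / 135 subjects in total.
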